3.2.1 Primary Objective Estimand

Table 1: Primary Objective Estimand

Objective	To evaluate the efficacy of rimegepant compared with placebo in the acute treatment of temporomandibular disorders on the time-weighted sum of pain intensity difference from baseline scores for the first 2 hours post-dose (SPID-2).
Efficacy Endpoint	Difference in SPID-2 scores between rimegepant and placebo groups assessed across the first 2 hours post-dose in treated subjects.
Summary	Difference in time-weighted SPID-2 between the rimegepant and placebo groups using an analysis of covariance (ANCOVA) model.
Intercurrent Events	
1) Use of non-study rescue medications on or before two hours post-dose
 
Composite strategy: All data points after rescue medication use are set to the last available observation prior to rescue medication usage when a subject uses a rescue medication on or before two hours post-dose. It is assumed that subjects who use rescue medication within the first two hours after dosing would not have experienced additional pain relief without the use of rescue medication.
 
2) Failure to log pain score at any time after study drug is administered through two hours post dose
 
Composite strategy: All missing data points are set to the last available observation for subjects that fail to enter pain score(s) in the eDiary any time on or before the two hour post-dose pain assessment. It is assumed that subject who fail to enter pain scores would not have experienced additional efficacy at the missing timepoints.
 
3) All other intercurrent events
 
Treatment policy strategy: All available assessments on the subject are used regardless of other intercurrent events.

3.2.2 Secondary Objective Estimands

Table 2: Secondary Objective Estimands

1	Objective	To evaluate rimegepant compared with placebo on the time-weighted sum of pain intensity difference (SPID) from baseline scores for the first 24 hours post-dose (SPID-24).
	Efficacy Endpoint	Difference in SPID-24 scores between rimegepant and placebo assessed across the first 24 hours post-dose in treated subjects
	Summary	Same as that of primary estimand, with respect to time-weighted SPID-24.
	Intercurrent Events	Same as that of primary estimand.
2	Objective	To evaluate rimegepant compared to placebo on change from baseline on NRS (0-10) score at 2 hours post-dose.
	Efficacy Endpoint	Change from baseline in NRS score to 2 hours post-dose in treated subjects.
	Summary	Difference in change from baseline in the NRS score between the rimegepant and placebo groups using a generalized linear mixed effect model.

	Intercurrent Events	Same as that of primary estimand.
3	Objective	To evaluate rimegepant compared to placebo on the proportion of subjects that are pain free at 2 hours post-dose.
	Efficacy Endpoint	The percentage of treated subjects that report no pain at 2 hours post-dose
	Summary	The difference between the rimegepant and placebo group in the percentage of subjects who are pain-free at 2 hours post-dose, analyzed using Mantel-Haenszel risk estimation. The definition of “pain free” is a subject that reports a zero on their 2 hour post-dose NRS assessment.
	Intercurrent Events	1) Use of non-study rescue medications on or before two hours post-dose Composite strategy: Subjects who use rescue medication on or before assessment of pain at two hours are imputed as a failure. 2) Failure to report eDiary assessments at two-hours post-dose Composite strategy: Subjects with missing data at two hours post-dose are imputed as a failure. 3) All other intercurrent events: Treatment policy strategy: All available assessments on the subject are used regardless of other intercurrent events.
4	Objective	To evaluate rimegepant compared to placebo on time to onset of meaningful pain relief post-dose.
	Efficacy Endpoint	The time to first nominal timepoint at which pain on NRS (0-10) decreases by 30% from baseline in treated subjects.
	Summary	Descriptive analysis by treatment group of the time to first nominal timepoint at which pain on NRS (0-10) decreases by 30% from baseline using Kaplan-Meier method. Meaningful pain reduction will be measured as a two-point reduction in NRS (0-10) score for subjects with a baseline pain score of 6, 7, or 8 and a 3 point reduction in NRS (0-10) score for subjects with a baseline pain score of 9 or 10.
	Intercurrent Events	1) Use of non-study rescue medications on or before onset of meaningful pain relief Composite strategy: Subjects who use rescue medication on or before onset of meaningful pain relief are censored at the time of rescue medication use. 2) Failure to report eDiary assessments. Composite strategy: Subjects who do not complete all post-dose assessment will be censored at the time of the last completed NRS pain assessment. 3) All other intercurrent events: Treatment policy strategy: All available assessments on the subject are used regardless of other intercurrent events.
5	Objective	To evaluate rimegepant compared to placebo on time to onset of initial pain relief post-dose.
	Efficacy Endpoint	The time to first nominal timepoint at which pain on NRS (0-10) decreases by 1 point from baseline in treated subjects.
	Summary	Descriptive analysis by treatment group of the time to first nominal timepoint at which pain on NRS (0-10) decreases by 1 point from baseline using the Kaplan-Meier method.

Intercurrent Events	Same as secondary endpoint # 4
---------------------	--------------------------------

6	Objective	To evaluate rimegepant compared to placebo on the probability of requiring rescue medication within 24 hours of initial treatment.
	Efficacy Endpoint	Percentage of treated subjects that use rescue medication within 24 hours after administration of study drug.
	Summary	The difference in the percentage of subjects that take study drug and then take rescue medication within 24 hours, analyzed using Mantel-Haenszel risk estimation.
	Intercurrent Events	Treatment policy strategy : All available assessments on the subject are used regardless of intercurrent events.

CCI [REDACTED]

[REDACTED]

[REDACTED]

[REDACTED]

[REDACTED]

[REDACTED]

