5.5 Daily and Rescue Medications and Oral Devices

Subjects may not use more than 1 of the following medications and not more than 1 of the oral devices if not otherwise prohibited by the protocol. Medication doses must be **stable**

within 3 months prior to the Screening Visit and throughout the study. Use of oral devices must be **consistent (i.e., non-active) within 3 months prior to the Screening Visit** and throughout the study.

Daily medications and therapy that are permitted during the study include:

- ! Tricyclic antidepressants (such as: amitriptyline, nortriptyline)
- ! Venlafaxine, desvenlafaxine, duloxetine, milnacipran
- ! Gabapentin, pregabalin
- ! Feverfew, magnesium (≥ 600 mg/day), riboflavin (≥ 100 mg/day)
- ! Botulinum therapy (e.g., onabotulinum toxin A, abobotulinum toxin A, and incobotulinum toxin A)

Oral devices that are permitted during the study include:

- ! Night guards, splints, dental orthotics, dental appliances
- ! Dental orthodontics

The use of CGRP antagonists (biologic [e.g., Aimovig®, Ajovi®, Emgality®, Vyepti®] or small molecule) other than rimegepant is prohibited during the study.

After dosing with study medication, all other pain medication is prohibited during the 2 hours post dose. However, a subject who does not experience relief of their pain at the end of 2 hours after dosing with study medication (and after the 2-hour assessments have been completed on the eDiary), will be permitted to use the following rescue medication: acetaminophen (up to 1000 mg/day); or aspirin, ibuprofen, naproxen (or any other type of non-steroidal anti-inflammatory [NSAID]), or cyclobenzaprine (all up to the daily recommended dose indicated on the drug packaging). Subjects may administer whichever protocol permitted standard of care rescue medication they choose to reduce symptoms and that they have available. These are the only medications allowed for rescue treatment after 2 hours post dose of study medication.

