9.4.2 Primary Endpoint(s)

The SPID-2 will be calculated by multiplying the PID score (difference between NRS at each time point and baseline NRS) at each post-dose timepoint by the duration (in hours) since the preceding timepoint, then summing the values over the 2 hours. This is analyzed on the treated population using an analysis of covariance (ANCOVA) model that includes the baseline NRS (0-10) value as a covariate, and main effects for treatment group and stratification factor (use of daily medications / oral devices to reduce the intensity of TMD symptoms).

The least squares mean (LS mean), standard error (SE), and 95% confidence interval (CI) for each treatment group will be reported, as well as the difference estimate (rimegepant - placebo), SE, 95% CI, and p-value.

Intercurrent events will be treated as failures, with the assumption that the subject does not improve once the intercurrent event occurs. In the event a subject uses a non-study rescue medication on or before 2 hours post-dose, all data points after rescue medication was administered will be set to the last available observation prior to rescue medication usage (RM = Rescue medication use: F = Failure). Likewise, if a subject fails to log their pain score at any time after study drug is administered, through 2 hours post-dose, this data will be imputed to the last available observation (NC = Non-completers; F = Failure).

Sensitivity analyses will be described in the SAP.

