9.4.3.2 Change from Baseline of Pain on NRS

The change from baseline of pain on NRS score at 2 hours post-dose will be analyzed with a generalized linear mixed effect model that includes subject as a random effect, the baseline NRS (0-10) value as a covariate, and fixed effects for treatment group, stratification factor (use of daily medications / oral devices to reduce the intensity of TMD symptoms), scheduled time point, and time point by treatment group interaction. Time points included in the model are nominally at 15, 30, 45, 60, 90 and 120 minutes post-dose. Repeated measurements within-subject will be modeled using an unstructured covariance structure for within-subject error. In the case that the model fails to converge, a Huynh-Feldt error structure will be attempted, followed by an AR(1) structure. Error degrees of freedom will be calculated using a Kenward-Roger approximation. The difference estimate (rimegepant - placebo), SE, 95% CI, and p-value will be reported for 2 hours post-dose.

Intercurrent events of use of a non-study rescue medication at or before 2 hours post-dose, or if a subject fails to log their pain score at any time after study drug is administered through 2 hours post-dose, will be handled in the same manner as they are for the primary endpoint.

9.4.3.3 *Pain Freedom at 2 Hours*

The number of subjects that are pain free at 2 hours post-dose will be analyzed after first imputing missing data at 2 hours to be failure (NC = F). Additionally, subjects who use rescue medication on or before assessment of pain at 2 hours will also be assigned as failures (RM = F). The analysis will be done using a stratified Cochran-Mantel-Haenszel (CMH) test after imputation is done, with the stratification factor as use of daily medications / oral devices to reduce the intensity of TMD symptoms.

9.4.3.4 *Time to Onset of Meaningful Pain Relief*

Time to onset of meaningful pain relief post-dose will be defined as the first nominal timepoint at which a 30% reduction of pain from baseline on NRS is achieved. This will be analyzed using Kaplan-Meier methods for a “time to event” analysis. Rimegepant will be compared to placebo using a log-rank test which will compare the survival distributions. Intercurrent events will be handled in the same manner as they are for the primary endpoint.

9.4.3.5 *Time to Onset of Initial Pain Relief*

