Time to onset of initial pain relief post-dose will be defined as the first nominal timepoint at which a 1-point reduction of pain from baseline on NRS is achieved. This will be analyzed using Kaplan-Meier methods for a “time to event” analysis. Rimegepant will be compared to placebo using a log-rank test which will compare the survival distributions. Intercurrent events will be handled in the same manner as they are for the primary endpoint.

9.4.3.6 *Rescue Medication Use through 24 Hours*

The number of subjects that use rescue medication through 24 hours post-dose will be analyzed using a stratified CMH test, with the stratification factor as use of daily medications/oral devices to reduce the intensity of TMD symptoms.

9.4.4 *Adjustment for Multiplicity*

Type 1 error is addressed in this study using a gatekeeping procedure. The significance of the primary endpoint is evaluated at the two-sided alpha level of 0.05. If the primary endpoint is significant, then the secondary endpoints are tested using Hochberg’s procedure.

CCI

9.4.5 *Missing Data*

For the primary and secondary endpoints of SPID-2, SPID-24, change in NRS from baseline, time to onset of meaningful pain relief, and time to onset of initial pain relief, subjects who fail to record their pain during the timeframe of interest for each endpoint will be considered

failures (NC = F) and this data will be imputed to the last available observation prior to the missing data occurrence.

For the secondary endpoint of proportion of subjects that are pain free at 2 hours post-dose, missing data at 2 hours post-dose will be imputed as a failure (NC = F), and these subjects will not be considered as having achieved pain freedom.

For the secondary endpoint of proportion of subjects who use rescue medication through 24 hours-post dose, there will be no imputation for missing data, the analysis will be based on non-missing, observed data.

Additional methods for handling of missing data, including sensitivity analyses, will be described in detail in the SAP.

9.4.6 *Rescue Medication*

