For the primary and secondary endpoints of SPID-2, SPID-24, change in NRS from baseline, time to onset of meaningful pain relief, and time to onset of initial pain relief, use of non-study rescue medications on or before the time point of interest (2 hours post-dose or 24 hours post-dose) will be handled as failures (RM = F). Specifically, the assumption will be that once the subject has used a rescue medication, their pain will not improve any further and these data points will be set to the last value recorded prior to the use of the rescue medication.

For the secondary endpoint of pain freedom at 2 hours post-dose, subjects that take rescue medication on or before the time point of interest (2 hours post-dose) will be considered as failures (RM = F).

Rescue medications are described in more detail in Section [5.5](#).

9.4.7 *Analysis of Safety*

The Investigators determine the intensity of AEs and the relationship of AEs to study therapy. The Investigators' terms are coded and grouped by system organ class using the latest version of the Medical Dictionary for Regulatory Activities (MedDRA) available. AEs are presented by system organ class and preferred term, ordered by the overall frequency of events. If a subject had an adverse event with different intensities over time, then only the greatest intensity is reported.

AEs are tabulated in all treated subjects. SAEs occurring in subjects enrolled but not treated are listed. Deaths are listed for enrolled subjects without regard to onset.

The frequencies of the following safety events are summarized by treatment regimen, and overall, for treated subjects: SAEs; all AEs, AEs by intensity; and AEs by relatedness.

Clinically significant laboratory test abnormalities will be identified as Grade 3 to 4 laboratory test results graded according to numeric laboratory test criteria in Common Terminology Criteria for Adverse Events (CTCAE) Version 5.0 (2017), if available. Otherwise, if CTCAE grades are not available, then results will be graded according to numeric laboratory test criteria in Division of AIDS (DAIDS) Table for Grading the Severity

of Adult and Pediatric Adverse Events Corrected Version 2.1 (2017). If a subject has a laboratory test abnormality with different toxicity grades over time, then only the highest toxicity grade will be reported.

Further safety analyses will be described in the statistical analysis plan.

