The survival distributions will be described at the nominal timepoints of 15, 30, 45, 60, 90, and 120 minutes, and 4, 8, and 24 hours post-dose. Subjects are considered to have an event through 24 hours if the first post-dose eDiary finding date/time where meaningful pain relief is achieved is (1) at or before the upper bound of the 24-hour analysis window in minutes (see [Table 5: Analysis Visit Windows for Safety Parameters](#)), and (2) is before the imputed rescue medication start date/time, if not missing (see Section 7.1). Subjects who do not have the event through 24 hours (even in the case of missing data) are censored at the earliest of the following: (1) upper bound of the 24-hour analysis window + 1 minute; (2) time from the study drug start date/time to the imputed rescue medication start date/time, if the time is at or before the upper bound of the 24-hour analysis window in minutes; (3) time from the study drug start date/time to the last non-missing eDiary date/time defining the endpoint, if the time was before the lower bound of the 24-hour analysis window in minutes. Likewise, subjects who take rescue medication will be censored at the time of first rescue medication use, if rescue medication is taken before meaningful pain relief is recorded.

A Kaplan-Meier (KM) plot and table using the following time intervals post-dose will be generated: using the following time intervals post-dose: 0 to 15, >15 to 30, > 30 to 45, > 45 to 60, > 60 to 90, > 90 to 120, > 120 to 180, > 180 to 240, > 240 to 360, > 360 to 495, and > 495 minutes. The KM plot displays the percentage of subjects with meaningful pain relief within 24 hours on the y-axis versus time in minutes on the x-axis. Refer to Core SAP for more details.

A time-to-event distribution table will be generated. This includes number and percentage of subjects with events; number and percentage of subjects censored in or before the last time interval; number and percentage of subjects censored in the last time interval; time-to-event median with 95% CI, first quartile, and third quartile. The 95% CI for the median is estimated using the method of Brookmeyer and Crowley.

6.3.3.5 *Time to Onset of Initial Pain Relief*

The analysis in Section 6.3.3.4 will be repeated with respect for the time to onset of initial pain relief. Initial pain relief will be defined as the timepoint at which a 1-point reduction of pain from baseline NRS is achieved.

6.3.3.6 *Rescue Medication Use within 24 Hours*

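### Time to pain relief: the SAP censors at rescue or at the last diary under a composite label, where the protocol counts failure, so late Kaplan-Meier relief is overstated

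*SAP*

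**What the plan says.** **Protocol.** Sections 9.4.3.4 (meaningful relief, a 30% reduction) and 9.4.3.5 (initial relief, 1 point) both state: "Intercurrent events will be handled in the same manner as they are for the primary endpoint". The primary rule in 9.4.2 is: "Intercurrent events will be treated as failures, with the assumption that the subject does not improve once the intercurrent event occurs". Sections 9.4.5 and 9.4.6 name both time-to-onset endpoints. Subjects who fail to record pain are "failures (NC = F) and this data will be imputed to the last available observation prior to the missing data occurrence". After rescue, the assumption is that "their pain will not improve any further and these data points will be set to the last value recorded prior to the use" of rescue.

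**SAP.** Table 2, objective 4, has two rules, each labelled a composite strategy. For rescue: "Subjects who use rescue medication on or before onset of meaningful pain relief are censored at the time of rescue medication use". For missing diaries: "Subjects who do not complete all post-dose assessment will be censored at the time of the last completed NRS pain assessment". Objective 5 takes over both. Section 6.3.3.4 puts them into the derivation ("subjects who take rescue medication will be censored at the time of first rescue medication use"), and 6.3.3.5 repeats that analysis.

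**Related SAP text.** Section 7.1.5 sets a dosing-day rescue with no recorded time to the dosing time, and names only 6.3.3.5 as the place where this is used. Section 6.3.3.3 counts the same subject as a failure for pain freedom. The SPID-24 row of Table 2 refers back to Table 1, whose rescue and missing-diary rules stop at two hours.

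**The concern.** If an unrelieved score is carried forward after rescue or after the last diary, that subject cannot have the event later and stays at risk without it. Censoring assumes something else: that the subject would go on to gain relief at the rate of those who remain. Protocol 5.5 makes this implausible for rescue, because it offers rescue to "a subject who does not experience relief of their pain at the end of 2 hours after dosing with study medication".

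The label adds to the confusion. Elsewhere in the SAP, a composite strategy means failure (pain freedom) or no further improvement (SPID-2). Here it covers a rule that behaves like a hypothetical strategy. The SAP says it is based on protocol version 3.0. Neither its revision history nor any other visible text declares a departure on this point.

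The late curve, the median and the quartiles of two secondary endpoints are at stake, and so is the apparent difference between arms.

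**Working it through.** **Plan's own figures.** There are none for these endpoints, and neither document gives a relief rate, a rescue rate or rescue timing. Every rate below is an assumption.

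**Direction.** Take the same relief events under both rules. Removing subjects from the risk set makes each later factor (1 − d/n) smaller, so Kaplan-Meier relief under censoring is never below that under the failure rule. It is strictly higher once any relief follows a censoring.

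**Size, rescue.** Let p be the share relieved by 2 h and U = 1 − p. A share r of U is rescued. The rest gain relief at rate q, in equal parts at 4, 8 and 24 h. Relief at 24 h is:

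- Failure rule: p + U(1−r)q
- Censored after the 2-h reading: 1 − U(1−q)
- After the 4-h reading: 1 − U[1−(1−r)q/3](1−q)/(1−q/3)
- After the 8-h reading: 1 − U[1−2(1−r)q/3](1−q)/(1−2q/3)

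Inputs: placebo p = 0.40, r = 0.30; rimegepant p = 0.50, r = 0.20; q = 0.50.

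| Rule | Placebo | Rimegepant | Difference |
|---|---|---|---|
| Failure | 0.40 + 0.60×0.70×0.50 = 61.0% | 0.50 + 0.50×0.80×0.50 = 70.0% | +9.0 |
| Censored after 2 h | 1 − 0.60×0.50 = 70.0% | 1 − 0.50×0.50 = 75.0% | +5.0 |
| Censored after 4 h | 1 − 0.60×0.8833×0.60 = 68.2% | 1 − 0.50×0.8667×0.60 = 74.0% | +5.8 |
| Censored after 8 h | 1 − 0.60×0.7667×0.75 = 65.5% | 1 − 0.50×0.7333×0.75 = 72.5% | +7.0 |

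The overstatement is 4.5 to 9.0 points on placebo and 2.5 to 5.0 on rimegepant. With q from 0.25 to 0.75 it is 1.8 to 13.5 and 1.0 to 7.5. If rescue is instead 20% on placebo and 30% on rimegepant (q = 0.50), the failure rule gives 64.0% and 67.5% (+3.5). Censoring then gives between +4.25 (67.0% and 71.25%) and +5.0 (70.0% and 75.0%). The distortion can therefore go either way.

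**Effect on the median.** Take 80 subjects, the planned arm size: 32 relieved by 2 h, 20 unrelieved subjects rescued between 2 and 4 h, then 6, 4 and 6 reliefs at 4, 8 and 24 h.

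- Censoring: 40.0% at 2 h; 1 − 0.6×22/28 = 52.9% at 4 h; 61.4% at 8 h; 1 − 0.6×12/28 = 74.3% at 24 h.
- Failure rule: 40.0%, 47.5%, 52.5% and 48/80 = 60.0%.

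The median moves from the 8-h to the 4-h diary.

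**Missing diaries.** With the same p and q, no rescue, and 10% of the unrelieved ceasing to log, censoring adds 3.0 and 2.5 points if the last diary is at 2 h. It adds 1.5 and 1.25 if the last diary is at 8 h. A last diary before 2 h raises the early curve too. Suppose that, in the 80-subject example, 20 are relieved by 60 min, 8 unrelieved subjects have their last diary then, and 12 more are relieved by 2 h. Relief at 2 h is 1 − (60/80)(40/52) = 42.3%, against 40.0%.

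**Untimed dosing-day rescue (7.1.5).** Such a subject is censored at time 0. Take 80 subjects, 40 with recorded relief by 2 h (50.0%), and 5 untimed rescues. The estimate is 35/75 = 46.7% if all five were relieved, because 6.3.3.4 requires relief before the imputed rescue time. It is 40/75 = 53.3% if none was. Kept at risk as failures, the same cases give 35/80 = 43.8% and 40/80 = 50.0%. Time-0 censoring is thus 2.9 to 3.3 points higher than the 6.3.3.3 convention.

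**The case against.** The protocol never says how a failure enters a Kaplan-Meier estimate, and it leaves full statistical detail to the SAP. Staying at risk to 24 hours is an inference. That is so, but it follows directly from carrying an unrelieved score forward, and leaving detail to the SAP does not permit reversing 9.4.5 and 9.4.6.

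The study was stopped early for low enrollment, and SAP section 5 evaluates no significance. Event percentages, censored counts and rescue use by arm are tabulated, so a careful reader can recover the crude proportion. This stands, and it limits the harm. But the curve, median and quartiles are the main output for these endpoints.

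The rates are assumed. Initial relief (1 point) is easier to reach, so fewer subjects remain unrelieved. With 70% and 75% relieved by 2 h, the largest excess, U×r×q, is 0.30×0.30×0.50 = 4.5 and 0.25×0.20×0.50 = 2.5 points. This also stands: the size is uncertain, the direction is not.

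On untimed rescue, keeping the subject as a failure turns relief recorded before the rescue into a non-event. In one of the two cases above, that moves the estimate further from the recorded 50.0% (46.7% to 43.8%). This is true. It is nevertheless how SAP 6.3.1 already treats untimed rescue for the primary endpoint, where it counts as used at every assessment from that date on. The SAP is not uniform, however: 6.3.3.6 excludes such subjects unless another timed use qualifies. This part, the cross-reference in 7.1.5 and the SPID-24 wording are minor.

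**Conclusion.** The concern holds and should be fixed. The SAP's censoring contradicts the protocol for both time-to-relief endpoints, carries the wrong strategy label and is not declared as a departure. Relative to the protocol's rule, late relief is overstated whenever relief events follow censoring at a timed rescue or a last diary. Under the main assumptions this is 4.5 to 9.0 points on placebo and 2.5 to 5.0 on rimegepant at 24 hours. Whether the difference between arms shrinks or grows depends on which arm has more rescue. Timed rescue taken as the protocol allows leaves the curve to 2 hours unchanged; early diary loss and untimed rescue can shift it. For untimed rescue the bias against recorded relief can go either way. No test or type I error is affected.

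**What to change.** 1. In SAP Table 2 (objectives 4 and 5) and 6.3.3.4/6.3.3.5, remove censoring at rescue and at the last diary: conditions (2) and (3) and the closing sentence that repeats the rescue rule. Keep subjects rescued before relief, and those who stop logging, at risk as non-events to the SAP's own end of follow-up, one minute past the 24-hour diary window (1500 + 1 = 1501 minutes, Table 5). If censoring is kept, call the strategy hypothetical and state it as a departure from protocol 9.4.5 and 9.4.6.
2. Count an untimed dosing-day rescue as a failure kept in the risk set, in line with 6.3.1 and 6.3.3.3. Change 1 does this with the existing 7.1.5 imputation. State that 7.1.5 serves 6.3.3.4 as well as 6.3.3.5.
3. In the SPID-24 row of Table 2, extend the rescue and missing-diary rules to 24 hours, as SAP 3.2, 6.3.2.1 with 6.3.3.1, and protocol 9.4.6 already imply.

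The cost is SAP wording and a simpler censoring derivation, with no new data. Late relief estimates will be lower, and at 24 hours will equal the crude event percentage already tabulated. Relief recorded before an untimed dosing-day rescue will not count as an event.
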